### Section 1 Regulatory Criterion for Approval: Risks are Minimized

**Risks to subjects are minimized: (i) by using procedures that are consistent with sound research design and that do not unnecessarily expose subjects to risk, and (ii) whenever appropriate, by using procedures already being performed on the subjects for diagnostic or treatment purposes.**

- Risks must be identified and classified as risks that would only be present if the subject participates in the research versus those risks that would happen as part of routine care or regardless of the subject's participation.
- ONLY evaluate the **research** risks and consider how to minimize those risks:
  - Is the question important scientifically/scholarly to answer?
  - Is the study designed so the question can be answered?
  - Can less risky procedures answer the question?
  - Can fewer procedures answer the question?
  - Are the procedures needed at all?
  - Can additional procedures reduce risk?
  - Can different eligibility criteria reduce risk?
  - Are investigators and key personnel adequately qualified relative to the activities being performed and are the activities within each individual's scope of practice?
  - Are procedures that will answer the scientific question being done anyway? If so, can the data from these procedures be used to reduce the likelihood or magnitude of harm?

## Protocol Summary/Submission Application

### Study Design

A. Has this proposal undergone separate formal review to determine appropriateness of study design (i.e. formal Scientific Review Committee)?

 No If NO, the IRB is responsible for determining that scientific design is appropriate
 
 Yes If YES, describe the entity and outcome of the review (provide minutes or supporting documents in the submission package, if available): Critical Care Research Operations Committee

B. Purpose of the study:

Evaluate the feasibility of using a percutaneous electrical nerve field stimulator (PENFS) for treatment of paroxysmal sympathetic hyperactivity (PSH) in children 2-17 years of age with acute severe brain injury (ASBI).

C. Hypothesis/specific aims:


Aim 1: Demonstrate the feasibility of use of PENFS to treat PSH, and tolerability of the device. Hypothesis: The PENFS device will be well tolerated, defined as < 10% early termination from the study. We will recruit 20 patients with ASBI and PSH who will receive PENFS therapy.
 
Aim 2a: Evaluate the feasibility of capturing pediatric PSH symptoms using the CFS scoring tool. Hypothesis: It is feasible to monitor the severity of PSH using a CFS scoring tool (Table 1a,1b). The scoring tool will be adapted for the appropriate age range of the patient (Table 2). We aim for at least 80% scoring (<math>\geq 8/10</math> scheduled scoring per protocol while the device is worn).
 
Aim 2b: Evaluate the effectiveness of the PENFS device in reducing PSH symptoms using change in CFS score. Hypothesis: A decrease in CFS severity score with use of PENFS will be associated with a lower number and/or doses of maintenance and rescue medications for control of PSH symptoms.
 
Aim 3a: Evaluate the change in autonomic balance with use of PENFS device Hypothesis: Heart Rate Variability (HRV) and pupillometry parameters that correspond to sympathetic and parasympathetic activity will be different after PENFS device placement compared to before, reflecting an increase in parasympathetic tone. All patients will be on routine continuous EKG monitoring in the PICU during the study period of interest. Similarly, pupillometry is routinely performed in patients with ASBI in the PICU.
 
Aim 3b: Evaluate feasibility of measuring PENFS effectiveness in treating PSH by a decrease in medication use. Hypothesis: It would be feasible to use the maintenance and rescue medication dosing and frequency as a marker of severity of PSH. PENFS device use will result in lesser number and/or doses of maintenance and rescue medications for control of PSH symptoms. We will compare the pilot sample to a historical cohort to allow power analysis and sample size calculation for a future larger efficacy trial, recognizing that this pilot study is not powered for efficacy.

D. Background, significance, and rationale (including description of preliminary studies and any results):


Paroxysmal sympathetic hyperactivity – incidence, pathophysiology, diagnosis, treatment, prognosis and implications for treatment Paroxysmal sympathetic hyperactivity is frequently seen in survivors of acute severe brain injury (ASBI). It is most commonly associated with severe traumatic brain injury (sTBI) with a reported incidence of 10-20% among survivors of sTBI (1-4,6-9). Survivors of anoxic brain injury have a higher incidence of PSH (approximately 30%) (5). The pathophysiology of PSH is incompletely understood. Current consensus is that it the result of disconnection between with neuroinhibitory higher centers in the diencephalon and the

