## Protocol Summary/Submission Application

One of the advantages of PENFS in the treatment of PSH is that it is continuously active while it is worn thus providing symptomatic treatment throughout that period. This could help prevent or ameliorate the paroxysmal symptoms classically seen in PSH and thus reduce the need for rescue medications. The device also has been shown to have a relatively rapid onset of action. A recent study showed that the onset of action was rapid with 63% reduction in narcotic withdrawal score within 20 minutes of activation of the device and 85% reduction within 60 minutes (26). Thus, PENFS could offer a non-pharmacological tool for managing PSH, helping to decrease the need for maintenance and rescue medications and thus limiting the side effects of some of these medications. Decreased need for neurosedative medications could further decrease the length of ICU stay for these patients thus decreasing healthcare costs. The device is also well-tolerated without any serious adverse effects (25).

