### **Aim 2a: Evaluate feasibility of scoring PSH symptoms using the PSH scoring tool**

**Methods:** The CFS (Table 1a) will be used to score the severity of PSH using the pediatric adaptation for the appropriate age range (Table 2 – diastolic blood pressure will not be used for scoring). CFS scoring will be performed by the bedside nurse who will be trained in using the scoring tool. PSH severity for the 12-hour period prior to placement of the device will be calculated retrospectively based on the features of CFS. After placement of the device, patients will be scored prospectively every 12 hours while the device is worn. The device will be discontinued after 120 hours of wear (usual duration of wear of a device). Scoring will be continued every 12 hours until 120 hours of device placement and then for another 72 hours (total of 192 hours for complete study duration). Every CFS score will be based on the severity of PSH symptoms in the preceding 12 hours.

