### Risks

**A. Describe potential research-related risks and discomforts (consider physical, psychological, legal, social/economic/financial, loss of confidentiality, group harms); describe the probability, magnitude, and duration of the potential risks; do not address risks that would be present if the individual did not participate:**

Local discomfort/pain, skin irritation. Theoretical risks include cardiac dysrhythmia and new-onset seizures neither of which have been reported in previous studies. In a randomized sham-controlled trial of the use of the device for 115 children with functional abdominal pain, only 1 patient among 60 with active device discontinued treatment due to discomfort, whereas 6 patients in the sham-group discontinued the device one being adhesive allergy. Patients will be monitored (including EKG monitoring at least in the initial 48 hours of the device) as inpatient during the time the device is in place. Other studies have also reported minimal to no side-effects using the device for other indications.

Other risks include remote possibility of loss of confidentiality if there is any breach of study data.

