## Protocol Summary/Submission Application

Verbal assent will be obtained and discussion documented in research records

**K. Describe the plan for obtaining legally effective informed consent and HIPAA Authorization at the age of majority [18] or describe why it is not applicable** (review **Guidance – Consent for Continued Participation When a Child Reaches Age 18** found in IRBNet under Forms and Templates):

Age of Majority Plan:

If a subject is in PICU and reaches the age of majority, we will assess already enrolled subject for their consent capacity during the time when device is already on the subject (active study participation phase). We do not anticipate the child will be conscious enough in this period and so, re-consent will be obtained from parent or legal guardian if subject is still in PICU. If the device has already been removed from the subject and the only study participation pertains to use of already collected data, we request a waiver of re-approach, consent and HIPAA authorization for continued use of data at the age of majority.

If the subject has already left PICU and there is no active study participation, no follow up contact will be made to subject or family as they are lost to follow up. The only study activity ongoing is continued use of their collected research data and we request waiver of consent and HIPAA authorization for continued use of this data, for the reason subject is lost to follow up.

**Contact the CW HRPP office to obtain appropriate supplements if you intend to enroll other vulnerable populations such as pregnant women, fetuses and neonates, prisoners (including incarcerated minors), or cognitively impaired adults.**

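### Aim 1 judges device tolerability by early exit from a 192 h study, although the device is worn for only 120 h; the event should be early removal of the device

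*Combined protocol and SAP*

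**What the plan says.** Section C (Hypothesis/specific aims, Aim 1) sets the criterion: "The PENFS device will be well tolerated, defined as < 10% early termination from the study". The Aim 1 methods in Section E restate it as a dropout rate of at most 10%, so the threshold is strict in one place and inclusive in the other.

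The Aim 2a methods end device wear at 120 h and continue 12-hourly scoring for 72 h more, a "total of 192 hours for complete study duration". Design & Methods enrols until 20 dyads complete. The denominator of the 10% is not stated.

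Section 7, item A allows withdrawal at any time, after which data collection stops. The analysis of Hypothesis 1 evaluates the reasons for early termination but does not limit the count to any of them. The Aim 1 methods also list nurse assessment of tolerance, the CFS score and skin integrity, none with a threshold.

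The evidence offered for good tolerability concerns the device. The Aim 1 methods cite a low rate of stopping it for side effects, and Risks, item A reports that "only 1 patient among 60 with active device discontinued treatment due to discomfort".

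**The concern.** The criterion counts leaving the study, whereas tolerability concerns whether the device stays on. The two can come apart in both directions.

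- **Counted although not intolerance.** A family that withdraws at 150 h, after a full 120 h of wear, has terminated early. So has a child who dies after planned removal. Neither event shows that the device was not tolerated.
- **Intolerance that need not be counted.** If the device is taken off at 24 h for a skin reaction and the child is still scored to 192 h, the child has not left the study. Nothing in the plan makes this an early termination.

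At stake is the only numerical tolerability criterion in the plan. It could be missed for reasons unrelated to the device, or met despite removals for intolerance. The study is unblinded, so leaving the event to be interpreted once the data are in would weaken the result as a basis for the next trial.

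**Working it through.** **Inputs from the protocol.** Wear 120 h and 72 h of further scoring (Aim 2a methods); thresholds < 10% (Section C, Aim 1) and ≤ 10% (Aim 1 methods); 20 children, a convenience sample (Section 6, item D); enrolment until 20 complete (Design & Methods); device discontinuation 1/60 = 1.7% (Risks, item A).

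**Assumed.** The probability e that a child leaves before 192 h for a reason unrelated to the device. The documents give no value; 5%, 10% and 15% are shown.

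**Study duration.** 120 + 72 = 192 h, as stated. The share after planned removal is 72/192 = 37.5%.

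**Exits the criterion allows.**
- < 10% of a fixed 20: one (2/20 is exactly 10%).
- ≤ 10% of a fixed 20: two.
- Everyone enrolled until 20 complete: two under either threshold, since 2/22 = 9.1% and 3/23 = 13.0%.

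**Chance of missing the criterion with a perfectly tolerated device (p = e).**
- Fixed 20, < 10%: 1 − [(1−p)^20 + 20p(1−p)^19]
- Fixed 20, ≤ 10%: as above, with 190p²(1−p)^18 added inside the bracket
- Enrol until 20 complete: 1 − (1−p)^20 × [1 + 20p + 210p²]

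At p = 0.10 the first is 1 − (0.122 + 0.270) = 0.608. The second is 1 − (0.122 + 0.270 + 0.285) = 0.323. The third is 1 − 0.1216 × 5.1 = 0.380.

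| Assumed e | < 10% of 20 | ≤ 10% of 20 | Enrol until 20 complete |
|---|---|---|---|
| 5% | 26% | 7.5% | 9.5% |
| 10% | 61% | 32% | 38% |
| 15% | 82% | 60% | 66% |

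**Adding intolerance at the cited rate.** With t = 1/60 and p = 1 − (1−t)(1−e), p is 6.6%, 11.5% and 16.4%. The chance of meeting < 10% of 20 is then 62%, 31% and 14%. Counting only removals for intolerance (p = 1/60), it is 95.7%, or 99.6% for ≤ 10%.

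**The opposite error.** Suppose 20% of children have the device removed early for intolerance and all are scored to 192 h. The study-level count is 0/20 and the criterion is met with certainty. A device-level count would meet < 10% of 20 with probability 0.069, and ≤ 10% with probability 0.206.

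**The case against.** The strongest reply is that the protocol probably means device discontinuation already. In the Aim 1 methods, the sentence just before the ≤ 10% threshold is about stopping the device for side effects, so dropout may be loose wording for that. This stands as evidence of intent and supports the fix, but the criterion as written in Section C still counts study exits.

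Second, tolerability does not rest on this count alone. Nurse assessment, skin checks, CFS scores, adverse events and reasons for termination are all collected or reported, and Section 6, item C has a stopping rule for five consecutive patients with device intolerance. A skin-related removal would therefore probably be visible. That stands too, and it would be too strong to say that Aim 1 cannot be answered. However, none of these items changes what enters the 10%.

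Third, all-cause termination with reasons listed is a defensible, conservative measure for a descriptive pilot with no go/no-go decision tied to the 10%. That is fair for feasibility, but not for a criterion labelled tolerability.

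A reader might go further and infer that PICU discharge counts as termination, so that a working device would count against itself. The text that suggests this does not establish it:
- "Decreased need for neurosedative medications could further decrease the length of ICU stay for these patients" is background expectation, with no length-of-stay figure.
- "If the subject has already left PICU and there is no active study participation, no follow up contact will be made" belongs to the age-of-majority plan (Section 8, item K) and applies only where participation is no longer active.
- Section 8, item C names the PICU as the location. Nothing there says that scoring stops on the ward.

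A reader might also infer that a child whose device comes off early is definitely kept in the study and counted as tolerant. The protocol describes no such pathway; it only fails to exclude it.

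**Conclusion.** The concern holds as a mismatch between the stated criterion and the question it is meant to answer. Section C counts exits from a 192 h study as device intolerance, over a third of that time lies after planned removal, and no other section corrects the count. Withdrawals and deaths after full wear are enough to establish the point; PICU transfer is only a possible further route.

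The size depends on three things that the protocol leaves open: the unrelated-exit rate, the threshold (< or ≤ 10%) and the denominator. At an assumed 10% of unrelated exits, the chance of missing the criterion with a perfectly tolerated device is 32% to 61% across the three readings. Quoting only the 61% would take the least favourable reading and ignore both the inclusive threshold in the Aim 1 methods and enrolment until 20 complete. The calculations treat exits as independent between children. The direction of the error does not depend on the reading chosen.

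This should be corrected, but it does not invalidate the pilot.

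**What to change.** In Section C (Aim 1), the Aim 1 methods and the analysis of Hypothesis 1:

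1. Define the tolerability event as device removal before 120 h, over all children in whom a device was placed, whether or not they are followed to 192 h.
2. Use removal for intolerance (discomfort, skin reaction or an adverse event attributed to the device) as the criterion, and report removal for any reason beside it.
3. Reconcile < 10% with ≤ 10% and use one threshold throughout.
4. Report study exit before 192 h by reason (withdrawal, death, transfer, other) as a separate feasibility count, and state how transfer out of the PICU is handled.

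The cost is protocol wording and one field for the time and reason of device removal, which neither Data collection & Management nor Table 3 now lists. No patients or procedures are added. The drawback is that attributing a removal to intolerance is an unblinded judgement, which is why the any-reason count is reported with it.

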### **E. Design and methods (including experimental design, technical details and laboratory methodology):**

#### **Design & Methods**

In this prospective unblinded pilot study we will enroll eligible patients until 20 parent/child dyads complete the study. It is expected many of the consented patients will not meet the eligibility criteria of CFS score > 6 (moderate severity of PSH). Those children will be considered Screen Failures and their parents/LAR told they are ineligible to continue in the study. Children admitted to the PICU at CW aged 2-17 years with ASBI and symptoms of PSH with a CFS score > 6 (moderate severity of PSH) will be eligible for inclusion. Exclusion criteria include age < 2 years (small ears thus less surface area to apply the leads), ear deformity or severe dermatitis of ear lobes, intractable seizures, heart block, patients with other implantable devices (cardiac pacemaker, vagal nerve stimulator, etc.) or known pregnancy.

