### **Aim 1: Identify and enroll 20 pediatric patients with ASBI and PSH.**

**Methods:** Parent(s)/legal guardians, 18 years or older, will be approached for informed consent if their child has ASBI and is exhibiting clinical signs and symptoms of PSH. Once consented, the CFS scoring tool (Table 1a,) will be used to evaluate patients felt to be exhibiting symptoms of PSH to identify eligible ASBI patients. Patients with CFS score > 6 will be eligible for enrollment in the study.

Families of patients who do not meet the CFS score criteria > 6 will be told their child did not meet scoring criteria of study and will be considered consented but not enrolled in study.

Study Enrollment is defined as meeting CFS criteria of > 6 after consent. If CFS scores are already being collected for subject prior to subject consent as a standard of care, we can use already available CFS scores from medical record. The PENFS device will be placed over the external ear by study investigator or one of trained nurses (RNs) from the Pediatric Translational Research Unit (P-TRU) within 24 hours of meeting CFS > 6 score criteria..

There are 380-400 PICU admissions/year that are seen by ICU Neurology. Using a conservative estimate of 8-10% incidence of PSH, we expect to have 35-40 patients with PSH. At a conservative 60% enrollment rate, we expect to be able to successfully enroll 20 patients in this pilot study. Previous studies using the device has shown it to be well-tolerated with minimal side effects (25,26). In a large, randomized sham-controlled trial Kovacic et al showed a very low rate of discontinuation of the device due to side effects. We hypothesize that the dropout rate will be ≤ 10%. Tolerability of the device will be assessed by subjective assessments of device tolerance by the bedside nurse, the CFS score (increasing score after device placement would suggest worsening PSH symptoms) and skin integrity (bedside nurses will perform routine skin evaluation and care while the device is in place.). To evaluate safety, we will monitor for serious adverse effects such as cardiac dysrhythmia (EKG monitoring), and new-onset seizures.

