## Protocol Summary/Submission Application

*Hypothesis 1:* The number approached and consented will be tracked. Reactions/ adverse events will be summarized and reasons for early termination, if any, evaluated.

*Hypothesis 2a, 2b:* The scoring tool will be adapted for the appropriate age range of the patient (Table 2). We aim for at least 80% scoring ( $\geq 8/10$  scheduled scoring per protocol while the device is worn). The association of the score and the number of doses of maintenance and rescue medications will be summarized with a spearman correlation and exact 95% Confidence intervals (CI).

*Hypothesis 3a:* HRV and Pupillometry measures will be tracked over time with any loss of data recorded with reasons. Wilcoxon Rank Sum test will be used to compare the mean  $\pm$ SD for the parameters for the 12-hour periods before and after device placement.

*Hypothesis 3b:* The number of doses of maintenance and rescue medications for control of PSH symptoms will be compared to historic data using a t-test or non-parametric Mann Whitney. Further a classification tree will be used to evaluate the effect of demographics, clinical history and use of PENFS.

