**D. Describe procedures to be employed in analyzing data (including a power analysis):**

*This is a pilot feasibility study of use of the device. A convenience sample of 20 patients was chosen.*

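### Aim 1 sets out to demonstrate under 10% early termination, but with about 20 children not even zero terminations excludes a true 10% rate at the 95% level by exact methods; no interval is planned, and threshold and denominator are each given two ways

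*Combined protocol and SAP*

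**What the plan says.** The first aim (Study Design, C. Hypothesis/specific aims, Aim 1) reads "Demonstrate the feasibility of use of PENFS to treat PSH, and tolerability of the device". Its hypothesis is "The PENFS device will be well tolerated, defined as" less than "10% early termination from the study", and it continues "We will recruit 20 patients with ASBI and PSH who will receive PENFS therapy".

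The Aim 1 Methods under E. Design and methods give the limit differently: "We hypothesize that the dropout rate will be ≤ 10" per cent. That version admits exactly 10%; the aim does not.

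Design & Methods sets the enrolment rule: "we will enroll eligible patients until 20 parent/child dyads complete the study". If children who stop early are replaced, more than 20 will be treated.

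For the analysis, Hypothesis 1 under Data analysis & interpretation says that numbers approached and consented will be tracked, events summarised, and "reasons for early termination, if any, evaluated". It gives no interval, error rate or decision rule for the 10% limit. Section 6, item D, which asks for a power analysis, answers "A convenience sample of 20 patients was chosen" and describes a pilot feasibility study.

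**The concern.** A numeric limit attached to an aim of demonstrating tolerability invites the report to say that the aim was met once the observed rate falls below the limit. With about 20 children, an observed rate below 10% is weak evidence about the true rate, and nothing in the planned output would tell the reader how weak. The result is meant to inform a larger trial in brain-injured children, so the uncertainty belongs beside the estimate.

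Two loose ends add to this. The strict and non-strict limits disagree at exactly 2 of 20. The choice between 20 recruited and 20 completing changes which counts meet the limit at all.

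**Working it through.** **Inputs.** Limit: under 10% (Aim 1) or at most 10% (Aim 1 Methods). Denominator: 20 recruited (Aim 1) or 20 + k, where k is the number terminating before 20 complete (Design & Methods). I take early termination and dropout to be the same event, and children to be independent with a common rate p. The protocol gives no confidence level; 95% is assumed, one- and two-sided. N = 20 is a convenience sample, so there is no sample-size calculation to reproduce.

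**Step 1: the best possible result.** For zero events in n, the exact (Clopper-Pearson) upper limit is 1 − α^(1/n).
- One-sided 95%: 1 − 0.05^(1/20) = 13.9%.
- Two-sided 95%: 1 − 0.025^(1/20) = 16.8%.
- Equivalently, a true 10% rate gives zero terminations with probability 0.9^20 = 0.122, above 0.05.

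The best result is 0/20 under either enrolment rule, so replacement does not change this. For scale only, zero events would exclude 10% at n = 29 one-sided (ln 0.05 / ln 0.9 = 28.4) or n = 36 two-sided (ln 0.025 / ln 0.9 = 35.01).

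**Step 2: exact two-sided 95% intervals.** Lower limit: the 0.025 quantile of Beta(x, n − x + 1), or 0 when x = 0. Upper limit: the 0.975 quantile of Beta(x + 1, n − x).

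| Terminations | Fixed 20 | 20 completers |
|---|---|---|
| 0 | 0/20: 0–16.8% | 0/20: 0–16.8% |
| 1 | 1/20: 0.1–24.9% | 1/21: 0.1–23.8% |
| 2 | 2/20: 1.2–31.7% | 2/22: 1.1–29.2% |

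**Step 3: which counts meet the limit.**
- Fixed 20, under 10%: at most 1 (1/20 = 5%; 2/20 = 10% fails).
- Fixed 20, at most 10%: at most 2.
- 20 completers: 2/22 = 9.1% meets both limits and 3/23 = 13.0% meets neither, so both mean at most 2.

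**Step 4: chance of meeting it.** For fixed 20, P(X ≤ c) is the sum over x ≤ c of C(20, x) p^x (1 − p)^(20 − x). For 20 completers, P(K ≤ 2) = (1 − p)^20 × (1 + 20p + 210p²).

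At p = 0.10:
- Fixed 20, at most 1: 0.1216 + 0.2702 = 0.392.
- Fixed 20, at most 2: 0.392 + 0.285 = 0.677.
- 20 completers, at most 2: 0.1216 × 5.1 = 0.620.

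| True rate | Fixed 20, under 10% | Fixed 20, at most 10% | 20 completers, either limit |
|---|---|---|---|
| 5% | 73.6% | 92.5% | 90.5% |
| 10% | 39% | 68% | 62% |
| 15% | 18% | 40% | 34% |
| 20% | 7% | 21% | 15% |

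A true 5% rate therefore misses the benchmark 26%, 7.5% or 9.5% of the time.

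**Step 5: sensitivity to method, for 0/20.** The exact one-sided 90% upper limit is 10.9% and the Wilson one-sided 95% limit is 11.9%, both still above 10%. The Jeffreys one-sided 95% limit is 9.0% and the Wilson one-sided 90% limit is 7.6%, both below it.

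**The case against.** This is a pilot with a convenience sample, and no test or success declaration is attached to the 10% figure. It can fairly be read as a descriptive benchmark on the observed rate. Tolerability is also judged by nurse assessment, CFS score and skin integrity, so termination is not the only evidence. Section 1 (Risks, item A) cites 1 discontinuation for discomfort among 60 children on the active device, or 1.7%.

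Much of this stands: no stated calculation is wrong, and 20 need not be increased. It does not settle the point. The aim speaks of demonstrating and defines the property by a number, and the statement that the pilot is not powered concerns efficacy only. The plan already promises exact 95% intervals for the Aim 2 correlation, so one for its first aim would be no departure in style. The 1-in-60 figure comes from children with functional abdominal pain, not brain-injured children in intensive care.

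A reader might infer more than the documents support:
- That the plan formally treats a point estimate under 10% as proof. It states no such rule; the gap is a strong verb with no interval behind it.
- That no method could exclude 10%. Step 5 shows that the statement needs its level and method named.
- That a device with a true 5% rate fails about a quarter of the time. That needs both a fixed 20 and the strict limit.
- That any passing result is compatible with one child in four stopping early. That is the upper limit for 1/20; for 0/20 it is about one in six.

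**Conclusion.** The point holds as a mismatch between the claim and what about 20 children can show. At the 95% level by exact methods, no result excludes a true 10% rate, and the planned summary would not show this. Meeting the benchmark is also only a loose screen: a true rate of 15% meets it 18% to 40% of the time, depending on which threshold and denominator are meant. The documents support both denominators, so neither set of pass rates can be called the plan's own. The figures rest on independent children, a common termination rate, and a 95% level that the protocol does not state.

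**What to change.** Keep the planned size and make these changes:

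1. In Aim 1, replace demonstrating tolerability with estimating it.
2. Define the denominator as every child who had the device placed, including any who are later replaced.
3. Use one threshold in Aim 1 and in the Aim 1 Methods.
4. Under Hypothesis 1, report the early-termination rate with its exact (Clopper-Pearson) 95% confidence interval.
5. State that an observed rate under the threshold is a go-forward signal, not evidence that the true rate is below 10%.
6. In Section 6, item D, add the expected precision for the chosen denominator, using the matching column of the Step 2 table.

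The cost is wording and one interval, with no extra patients. The downside is that the stated claim becomes less favourable.
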